1.3.2 Subject Diary Card

Subjects will be asked to record their assessment of study treatment response in a diary card on Day 0 (baseline post-treatment) through Day 7. They will be asked to respond “Yes” or “No” to the following question:

- *“Since being injected have you noticed an improvement in the appearance of your glabellar lines (lines between your eyebrows) when you frown?”*

Subjects will complete the diary card daily, starting on the day of treatment (Day 0), and will return the diary to study site at their Month 1 visit.

For each subject, time, in days, to onset of treatment response will be computed. A flag will be created to determine the diary date of when the subject first answers 'Yes' to "Since being injected have you noticed an improvement in the appearance of your glabellar lines (lines between your eyebrows) when you frown?" Time, in days, to onset of treatment response will be calculated as follows:

$$\text{Number of days to onset} = \text{Date of Diary Flag} - \text{Date of Day 0}$$

Subjects who never notice an improvement will be censored at Day 7. Subjects dropping out before noticing improvement will also be censored at Day 7 or date of withdrawal, whichever comes first. Subjects who never return their diary will be censored on Day 7.

[figure not shown]
CCI

Sponsor: *Galderma*

Protocol Number: *43QM2106*

Plan Version: *V1.0*

CCI

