7.1.2 Subject Diary Card

Subjects will be asked to record their assessment of study treatment response in a diary card on Days 0 through 7 post-treatment. They will be asked to respond “yes” or “no” to the following question:

“Since being injected have you noticed an improvement in the appearance of your glabellar lines (lines between your eyebrows) when you frown?”

Subjects are to complete the diary card daily, starting on the day of treatment (Day 0), and return the diary to study center at their Month 1 visit.

CCI

[figure not shown]

[figure not shown]
[figure not shown]
Effective date: 2022-03-21 13:08

Effective

Version: 3.0

CCI

 EST. 1981	Title 43QM2106 Clinical Study Protocol – QM1114 – GL	Doc id MA-49290

CCI
 		

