2.4.2 Handling of missing data

In general, the number of subjects with missing values will be summarized and reported as appropriate in all outputs. The primary analysis will be performed using the result of 'No Change' for any missing Month 1 GAIS assessment as the primary imputation method.

In addition, to further evaluate the impact of missing data on the primary endpoint, additional sensitivity analyses will be performed:

1. The primary analysis will be repeated using multiple imputation (MI) based on the ITT population
2. The primary analysis will be repeated using Observed Cases (OC) based on the ITT population (i.e., no imputation will be done)

The secondary efficacy analyses, exploratory analyses and safety analyses will be performed using OC. If deemed necessary, any analyses may be repeated using OC, 'No Change' imputation, baseline observation carried forward (BOCF), or MI as appropriate. Calculations for the FACE-Q and FLTSQ will follow the methods specified in the manuals for the handling of the data.

Missing data for Month 1 GAIS responses will be imputed using the following steps:

1. The imputation using MI will assume the Missing Completely at Random (MCAR) missing data assumption. Regardless of the actual pattern of missing data, the Markov Chain Monte Carlo (MCMC) method of the MI procedure from the SAS® system will first be used to create a monotonic pattern of missing data. The minimum values for imputed variables will be set to 0, in order to force PROC MI to redraw another value for imputation when an intended imputed value is less than the 0. The maximum value for imputed variables will be

set to 6, in order to force PROC MI to redraw another value for imputation when an intended imputed value is greater than 6. Imputed values will be rounded to the nearest integer. The seed number to be used will be the number 110196.

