2.4.5.1 Secondary Efficacy Estimands

The estimands of the secondary endpoints can be written out in a similar manner as the estimand of the primary endpoint. Secondary endpoints share the following attributes of estimands:

Population: all randomized subjects (ITT population)	
Intercurrent Events: 
1. Missing observations for assessments2. Administered treatment not according to randomization3. Use of prohibited treatment in or near treatment area between 9 months prior to study treatment and prior to study end4. History or presence of eyelid or eyebrow ptosis at Baseline	
1. Use observed cases, leave response missing.2. Use observed response.3. Use observed response.4. Use observed response.

High-level descriptions of summary measures for the secondary efficacy endpoints are outlined below:

- Time to onset of treatment effect:
 - Endpoint: Onset of effect is defined as the first day a subject answers “yes” to the diary question.
 - Summary measure: descriptive statistics of time-to-event of subject responding “yes” to the diary question for QM1114-DP and placebo.
- GAIS responder rate:
 - Endpoint: Responder rate based on the 7-point GAIS where a responder is defined as a subject who responds at least “Improved” on the GAIS at maximum frown.
 - Summary measure: descriptive statistics of proportion of subjects that have at least “Improved” for QM1114-DP and placebo by visit.

[figure not shown]
CCI

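### Diaries that are never returned are censored at Day 7 as if 'no' had been recorded throughout, which lowers the onset curve and can move the median later

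*SAP*

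**What the plan says.** SAP section 1.3.2 has subjects answer one yes/no question in a "diary card on Day 0 (baseline post-treatment) through Day 7", which makes eight daily entries. Onset is the date of the first 'yes' minus the date of Day 0. Three rules cover subjects without a 'yes':

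- For a subject followed to the end of the diary with no 'yes', the rule is: "Subjects who never notice an improvement will be censored at Day 7".
- A dropout with no 'yes' is censored at withdrawal, or at Day 7 if that is earlier.
- For a missing diary, the rule is: "Subjects who never return their diary will be censored on Day 7".

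The card is not collected when it is finished. Subjects "will return the diary to study site at their Month 1 visit", and Protocol section 7.1.2 agrees: "return the diary to study center at their Month 1 visit". Protocol section 9.1.3 plans Kaplan-Meier plots and a median for time to onset.

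On missing data, SAP section 2.4.2 says: "The secondary efficacy analyses, exploratory analyses and safety analyses will be performed using OC". SAP section 2.4.5.1 lists attributes shared by the secondary estimands, time to onset included, and for missing observations says: "Use observed cases, leave response missing". SAP section 2.4.5 also sets observed cases as the default for secondary analyses but allows exceptions where specified. Section 2.4.5.2 is redacted in the public copy.

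**The concern.** A diary that never comes back says nothing about when improvement was noticed. Kaplan-Meier treats a subject as at risk and event-free up to the censoring time, so censoring at Day 7 asserts that no improvement was noticed from Day 0 to Day 7. That amounts to imputing 'no' for the whole diary period.

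The situation is foreseeable. The schedule of assessments counts a month as 4 weeks, so the card is due about 28 - 7 = 21 days after its last entry. Anyone lost in that interval, or who mislays the card, falls under the rule. Subjects also rate the GAIS in clinic on Days 1 to 4. A non-returner could therefore have rated 'Improved' on Day 2 and still be analysed as free of onset through Day 7.

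What is at stake is how onset is described. Onset is in the trial title, in the study objective and in the clinical hypothesis. The median is a whole number of days, so a shift of one day would be visible in the report.

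**Working it through.** **Inputs from the documents.** The diary runs over Days 0 to 7, with the three censoring rules above (SAP 1.3.2). The estimator is Kaplan-Meier with a median (Protocol 9.1.3). The arms are 90 active and 30 placebo (Protocol 9.2). The documents give no onset curve, median or diary-return rate that could be reproduced, and the sample-size text is redacted. All return rates and onset curves below are assumptions.

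**Step 1: the records compared.**

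| Subject | What was observed | Record under SAP 1.3.2 |
|---|---|---|
| Diary complete, 'no' on Days 0-7 | eight answers | time 7, no event |
| Diary never returned | nothing | time 7, no event |
| Withdraws on Day 3, diary not returned | nothing | Day 3 under the dropout rule, Day 7 under the non-return rule |

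The first two records are identical. The third subject meets two rules that give different times.

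**Step 2: effect on the curve.** Let F(t) be cumulative onset among returners. With no censoring before Day 7, Kaplan-Meier equals events so far divided by N. Non-returners add to N but not to the events:

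reported onset(t) = N(1-m)F(t) / N = (1-m)F(t)

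The curve therefore cannot exceed 1-m. For an assumed F(7) of 95%:

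- m = 5%: 0.95 x 0.95 = 90%
- m = 10%: 0.90 x 0.95 = 86%
- m = 15%: 0.85 x 0.95 = 81%

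**Step 3: effect on the median.** The median moves later when (1-m)F < 0.5 at the true median day, that is, when F on that day lies between 0.5 and 0.5/(1-m):

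| m | Median moves if F at the true median day is below |
|---|---|
| 5% | 0.5/0.95 = 0.526 |
| 10% | 0.5/0.90 = 0.556 |
| 15% | 0.5/0.85 = 0.588 |
| 20% | 0.5/0.80 = 0.625 |

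**Step 4: worked active arms, N = 90.** Counts are rounded to whole subjects.

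| Assumed curve | Not returned | Onset on that day, returners only | Onset on that day, SAP rule | Median, returners / SAP rule |
|---|---|---|---|---|
| F(2) = 52% | 5 (5.6%) | 44/85 = 51.8% | 44/90 = 48.9% | Day 2 / Day 3 |
| F(2) = 52% | 9 (10%) | 42/81 = 51.9% | 42/90 = 46.7% | Day 2 / Day 3 |
| F(4) = 54% | 9 (10%) | 44/81 = 54.3% | 44/90 = 48.9% | Day 4 / Day 5 |
| F(2) = 60% | 14 (15.6%) | 46/76 = 60.5% | 46/90 = 51.1% | Day 2 / Day 2 |
| F(2) = 60% | 18 (20%) | 43/72 = 59.7% | 43/90 = 47.8% | Day 2 / Day 3 |

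**Step 5: sampling variation.** Each scenario used 1,500 simulated arms of 90, with non-return independent of onset, over four assumed curves. The chance that the median was delayed by at least one day was 5-22% at m = 5%, 17-46% at 10%, 33-68% at 15% and 53-86% at 20%. The median never moved earlier. A shift of two days or more occurred in at most 0.7% of arms at m = 10% or less, and reached 22% only for the slowest curve at m = 20%.

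**Step 6: comparison of arms.** Assume F(7) of 93% on active and 16% on placebo, a true difference of 77 points.

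- m = 10% in both arms: 0.90 x 77 = 69.3 points, so the difference shrinks.
- m = 20% on placebo only: 93 - 0.80 x 16 = 80.2 points, a widening of 3.2.
- m = 20% on active only: 0.80 x 93 - 16 = 58.4 points.

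With 16% placebo onset, the placebo median is not reached under any of the rules.

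**The case against.** The strongest defence is that the rule keeps all randomized subjects in the analysis and counts unknown onset against the product. Onset is secondary and descriptive (Protocol 9.1.5, SAP 2.4.5.1), and the visible text attaches no test or power to it. If every non-returner truly had no onset by Day 7, the rule would cause no bias. Excluding non-returners carries its own risk: if subjects without benefit return fewer diaries, exclusion makes active onset look faster. All of this stands. It limits the seriousness of the point and is a reason to keep the rule as a sensitivity analysis. It does not justify recording unobserved days as observed in the main estimate.

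A reader might also infer stronger claims that the documents do not support:

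- *That the SAP flatly contradicts itself.* The Day 7 rule fits poorly with leaving responses missing, but section 2.4.5 allows exceptions to observed cases, and section 1.3.2 can be read as one.
- *That no sensitivity analysis exists.* The only secondary endpoints are onset and GAIS, and section 2.4.5.3 covers GAIS. The redacted section 2.4.5.2 therefore probably holds the onset analysis, and its content cannot be judged. Section 2.4.2 also permits repeat analyses if deemed necessary.
- *That the dropout rule has the same fault.* Censoring at withdrawal before Day 7 is reasonable, and Day 7 is right for a later withdrawal whose returned diary shows 'no' through Day 7. Only the missing diary is the problem.
- *That the rule favours the product.* Under the Step 6 assumptions, even 20% non-return confined to placebo widens the difference by only 3.2 points.

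**Conclusion.** The point holds as a flaw in the stated derivation. Followed exactly, SAP 1.3.2 treats absent data as eight days without onset and multiplies the curve by (1-m). That factor is exact if non-return is unrelated to onset and there is no earlier censoring.

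A later median is possible but not certain. It depends on m and on how close the curve is to 50% at the median day, and the documents give neither. At m = 5% a delay is the less likely outcome on every curve tried; by m = 20% it is more likely than not.

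The primary endpoint, the safety analyses and the sample size are unaffected. The distortion falls mainly on the active-arm curve and median, and it works against the product. This should be fixed before database lock, but it does not threaten the trial's main conclusion.

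**What to change.** Amend SAP section 1.3.2 as follows:

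1. Censor a subject without a 'yes' at the last day with a diary answer. Use Day 7 only when answers run through Day 7.
2. Treat a subject with no diary entries as missing and leave that subject out of the Kaplan-Meier estimate. Do not censor at Day 0: Day 0 is itself an assessment day, so the subject would remain in the Day 0 risk set.
3. Report the number of subjects without diary entries by arm.
4. Keep the present Day 7 rule as a labelled conservative sensitivity analysis on all ITT subjects.
5. Cross-refer sections 2.4.2 and 2.4.5.1 to this rule, so that onset has a single missing-data instruction.

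The change takes a few sentences and one derivation. It costs a slightly smaller N and an assumption that non-returners resemble returners. The retained sensitivity analysis shows how far the result depends on that assumption, and the clinic GAIS ratings from Days 1 to 4 give an indirect check on it.

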1.4 Efficacy endpoints

For all endpoints using responder rate, the responder rate is defined as $\frac{m}{n} \times 100$ where m is the number of responder subjects and n is the total number of subjects in the ITT population.

For all endpoints using proportion, the proportion will be calculated as $\frac{m}{n} \times 100$ where m is the number of subjects reporting the specified values on each question of the specified efficacy assessment at each visit, and n is the total number of subjects in the ITT population.

Percent of subjects in each response category will be calculated as $\frac{m}{n} \times 100$ where m is the number of subjects in each response category and n is the number of subjects

The definition of n will change based on the population used in the output.

1.4.1 Primary efficacy endpoint

The primary efficacy endpoint is the responder rate based on the 7-point GAIS at Month 1. A responder is defined in [Section 1.3.1](#).

1.4.2 Secondary efficacy endpoints

Secondary endpoints include:

- (i) Time (days) to onset of treatment effect following a single dose of QM1114-DP and placebo based on the subject's diary card. Derivation of the endpoint is described in [Section 1.3.2](#).
- (ii) Responder rate based on the 7-point GAIS at each post-treatment visit at maximum frown. Responder is defined as a subject who respond "Improved", "Much improved", or "Very much improved".

1.5 Safety assessments and endpoints

For details regarding the safety assessments, please refer to Section 7.2 of the Protocol.

1.5.1 Adverse events

Adverse events (AEs) are to be monitored throughout the course of the study. All AEs reported will be coded using the Medical Dictionary for Regulatory Activities (MedDRA, Version 25.0 – March 2022 or higher) and classified by MedDRA preferred term (PT) and system organ class (SOC). AEs will be defined as treatment-emergent adverse events (TEAEs) if the AE had an onset time greater than or equal to the time of study treatment. The study period for the purpose of AE collection is defined as the period from the signing of a study specific informed consent to study exit.

A two-point scale (“Yes” or “No” response) will be used for the causality assessments. The Treating Investigator should be asked to indicate a response to each of the following questions in the electronic Case Report Form (eCRF):

- “Do you consider that there is a reasonable possibility that the event may have been caused by the study product?”
- “Do you consider that there is a reasonable possibility that the event may have been caused by the study product injection procedure?”

If either of these questions is answered with a ‘Yes’, the AE will be considered related.

All AEs will be monitored by the Sponsor to determine if they meet the criteria of remote spread of effect of the toxin or hypersensitivity, which will be included as an AE endpoint. A list of preferred terms for these types of events will be analyzed to determine if there is a plausible possibility that they represent remote spread of toxin or hypersensitivity. The Sponsor will consider variables including alternative etiology (medical history, concomitant medications, or diagnosis which could account for the symptoms), location of QM1114-DP administration, and temporal relationship to

QM1114-DP administration in order to perform the analysis. Sponsor determination will be cross-referenced with Investigator-reported potential remote spread of the toxin or hypersensitivity AEs. Before unblinding the subject data, and as a part of preparations for the database lock, the study team will review and adjudicate all AEs to create a finalized list of remote spread of toxin or toxin hypersensitivity events for the analysis.

Refer to Galderma Work Instruction QMS-13549 effective 16MAR2022 and to the Data Management Plan V1.0 for more details on this process.

AE endpoints include incidence and severity of TEAEs.

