7.2.4.1 Definitions

7.2.4.1.1 Adverse Events

According to International Council for Harmonisation (ICH) E2A,¹⁵ an AE is any untoward medical occurrence in a patient or a clinical investigation subject administered a pharmaceutical product and which does not necessarily have a causal relationship with this treatment. An AE can therefore be any unfavorable and unintended sign (including an abnormal laboratory finding), symptom, or disease temporally associated with the use of a medicinal (investigational) product, whether or not related to the medicinal (investigational) product.

Thus, any new sign, symptom or disease, or any clinically significant worsening of an existing sign, symptom or disease (including new episodes of a chronic disease [e.g., hay fever, allergy]) compared to the condition at the first visit, should be considered as an AE. Lack of efficacy is not considered as an AE.

Notes:

- There should be an attempt to report a diagnosis rather than the signs, symptoms or abnormal laboratory values associated with the report of an AE. However, a diagnosis should be reported only if, in the investigator's judgment, it is relatively certain. Otherwise, symptoms, signs, or laboratory values should be used to describe the AE.
- Pregnancy is not to be considered as an AE; however, is an important medical event that must be monitored as described in Section 7.2.4.2.3.

 EST. 1981	Title 43QM2106 Clinical Study Protocol – QM1114 – GL	Doc id MA-49290
---	--	---------------------------

- The effects of all BoNT products may spread from the area of injection to produce symptoms consistent with BoNT effects. These symptoms have been reported hours to weeks after injection. Remote spread of toxin that affects swallowing and breathing can be life threatening, and there have been reports of death. The risk of symptoms is increased in subjects who have underlying conditions (e.g. disorders of the neuromuscular junction) that would predispose them to these symptoms. BoNT is contraindicated in individuals with known hypersensitivity to any BoNT preparation or to any of the components in the formulation.

7.2.4.1.2 *Treatment Emergent Adverse Event*

A TEAE is an event that emerges during or after treatment, having been absent pre-treatment, or worsens relative to the pre-treatment state.

7.2.4.1.3 *Serious Adverse Events*

A SAE is any untoward medical occurrence that at any dose:

- Results in death,
- Is life-threatening,

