9.1.3.1 Safety Analysis

All treatment related TEAEs by maximum intensity, treatment unrelated TEAEs by maximum intensity, treatment emergent SAEs by causality and maximum intensity, and action taken of treatment related TEAEs will be summarized by system organ class (SOC) and preferred term (PT) including number of subjects with at least one event, percentages, and number of events. All related TEAEs will also be summarized by time to onset and duration. In addition, a short summary of the analysis of TEAEs will be provided. AEs occurring before treatment will only be provided in subject data listings.

Data for vital signs will be summarized by descriptive statistics with the value at each visit as well as the change from baseline. The number and percentage of subjects with normal/abnormal results in physical examination will be presented by visit and treatment. A shift table will be created to present any change from baseline in normal/abnormal results in physical examination across the study visits for each treatment group. The results of the urine pregnancy tests will be listed.

All AEs will be monitored by the Sponsor to determine if they meet the criteria of remote spread of effect of the toxin or hypersensitivity. A list of preferred terms for these types of events will be referenced to in the DMP and will be further analyzed to determine if there is a plausible possibility that they represent remote spread of toxin or hypersensitivity. In order to perform the analysis, variables including alternative etiology (medical history, concomitant medication, or diagnosis which could account for the symptoms), location of QM1114-DP administration, and temporal relationship to QM1114-DP administration will be considered by the Sponsor.

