2.5.2 Adverse events

All AE data will be summarized by treatment group. Missing dates will be imputed as described below. AEs will be summarized by SOC and PT. AEs occurring before treatment will be presented in listings only. The MedDRA version used for the coding will be noted as a footnote in the tables and listings. In general, percentages for the number of subjects will be calculated using the number of subjects in the safety population for the denominator.

A summary of all AEs will be provided, which will include:

- number (%) of subjects who did not have an AE
- number (%) of subjects with at least one TEAE and number of events
- number (%) of subjects and events with at least one TEAE related to study product or injection procedure and number of events
- number (%) of subjects and events with at least one TEAE not related to study product or injection procedure and number of events
- number (%) of subjects and events with at least one TEAE leading to discontinuation and number of events
- number (%) of subjects and events with at least one serious TEAE and number of events
- number (%) of subjects and events with at least one serious related TEAE and number of events
- number (%) of subjects and events with at least one AE that meets the criteria of remote spread of effect of toxin or hypersensitivity and number of events

Summaries of TEAEs (including the total number of events, number and percentage of subjects) will be displayed by treatment group according to the following:

- All TEAEs by SOC and PT
- Treatment emergent SAE by SOC, PT, maximum intensity (mild, moderate, severe), and causality
- Related TEAEs by SOC and PT, and maximum intensity (mild, moderate, severe)
- Unrelated TEAEs by SOC and PT, and maximum intensity (mild, moderate, severe)
- TEAEs leading to discontinuation by SOC and PT, and maximum intensity (mild, moderate, severe)
- TEAEs by SOC, PT, and action taken (none, medical treatment, non-pharmacological treatment, subject withdrawn)
- TEAEs that meet the criteria of remote spread of effect of toxin or hypersensitivity by SOC, PT, and maximum intensity (See [Section 2.5.2.2](#))

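### The SAP's TEAE rule omits the protocol's worsening limb, so an AE that starts before injection and worsens afterwards can be left out of the TEAE summaries

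*SAP*

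**What the plan says.** Protocol 7.2.4.1.2 gives the definition in two limbs: "A TEAE is an event that emerges during or after treatment, having been absent pre-treatment, or worsens relative to the pre-treatment state".

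SAP 1.5.1 gives one: an AE is a TEAE "if the AE had an onset time greater than or equal to the time of study treatment". The same section sets the AE collection period as "the period from the signing of a study specific informed consent to study exit", so AEs can be on record before any treatment is given. Protocol 8.1.1 allows up to 14 days between screening and baseline, and lets the two visits fall on the same day.

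SAP 2.5.2 builds its system organ class and preferred term summaries on TEAEs and adds: "AEs occurring before treatment will be presented in listings only". Protocol 9.1.3.1 says the same: "AEs occurring before treatment will only be provided in subject data listings".

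Incidence and severity of TEAEs is the first endpoint listed in Protocol 2.1.4 and the AE endpoint named in SAP 1.5.1.

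**The concern.** The SAP is meant to carry out the protocol's analyses in more detail (Protocol 9.1). Here it narrows the definition behind a named safety endpoint and gives no reason. A programmer working from SAP 1.5.1 would set the flag from the onset date and time alone. SAP 2.1.2 confirms this, since it says its date rules are used to work out treatment emergence.

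The exposed case is specific. An AE arises after consent and before injection, is still ongoing at injection, gets worse afterwards and is kept as one record. It is a TEAE under the protocol and not under the SAP. If it became severe, serious or product-related only after injection, it would still be missing from the summaries meant to show that.

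**Working it through.** **1. The two definitions side by side**

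| Situation | Protocol 7.2.4.1.2 | SAP 1.5.1 |
|---|---|---|
| Absent before treatment, starts at or after it | TEAE | TEAE |
| Starts before treatment, does not worsen | Not a TEAE | Not a TEAE |
| Starts before treatment, worsens after it, entered as a new AE | TEAE | TEAE (the new record has a later onset) |
| Starts before treatment, worsens after it, kept as one record | TEAE | Not a TEAE |

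Only the last row differs. The listings-only sentence is common to both documents, so it is not the source of the difference. It matters because the SAP's narrower definition sends that last row to the listings.

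**2. Does anything in the SAP restore the second limb?** SAP 1.5 has a general pointer: "For details regarding the safety assessments, please refer to Section 7.2 of the Protocol". Protocol 7.2 does contain the two-limb definition. But the pointer concerns how assessments are made, and an explicit onset-only rule follows it in SAP 1.5.1. The explicit rule is the one that would be programmed.

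**3. Is a worsening certain to become a new record?** Protocol 7.2.4.1.1 treats as an AE "any clinically significant worsening of an existing sign, symptom or disease", judged against the condition at the first visit. That covers a condition already present at consent. For an AE that arose after the first visit, it does not say whether later worsening opens a second record or changes the severity on the first. Protocol 7.2.4.2.1 lists onset date and severity among the items on the AE form, but no date of worsening. The question is left open.

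**4. Which outputs use the flag?**
- Tied to TEAEs (SAP 2.5.2): all TEAEs; related and unrelated TEAEs by maximum intensity; TEAEs leading to discontinuation; action taken; treatment-emergent SAEs; onset and duration of related TEAEs.
- Worded AE: the no-AE row and the remote-spread or hypersensitivity row of the overview (SAP 2.5.2), and the table by antibody category (SAP 2.5.3). The listings-only sentence may or may not apply to these.
- Independent of the flag: the physical-examination shift table and the vital-sign changes (SAP 2.5.4), and the data listings.

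**5. Size.** The documents give no figure to reproduce for this point.
- Pre-treatment AE time is at most 14 days. Follow-up is 12 × 28 = 336 days, as the schedule sets one month at four weeks. The share is 14 / (14 + 336) = 14/350 = 4% at most, and close to zero when screening and baseline fall on the same day.
- One subject with no other TEAE moves overall incidence by 1/90 = 1.1 points (active) or 1/30 = 3.3 points (placebo), taking the planned arm sizes as the safety population.
- The documents give no rate for such events. At assumed rates of 0.5%, 1%, 2% and 5% of subjects, the expected number among 120 is 0.6, 1.2, 2.4 and 6.0.

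**6. Direction.** Omitting the limb can only remove events. SAP 2.1.2 works the other way. A completely missing start date is set to the treatment date. A start date with only the day missing is set to the treatment date whenever the first of that month falls before it. Some true pre-treatment AEs can therefore enter the TEAE set.

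**The case against.** The strongest reply is that other rules already catch most worsening. A condition present at consent is medical history, and its clinically significant worsening is an AE under Protocol 7.2.4.1.1, with an onset after injection. Protocol 7.2.1 and 7.2.2 require clinically significant post-injection examination abnormalities, and clinically significant changes in vital signs from baseline, to be recorded as AEs. Clinically significant examination findings at screening or baseline exclude the subject (Protocol 5.2.2, criterion 6). Completion guidance for the eCRF, which is not among the documents, may already ask for a new record. All safety outputs are descriptive (Protocol 9.1.5, SAP 2.5), so no test depends on this.

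Most of this stands, and it makes the affected group small. It does not remove the contradiction. It leaves the outcome to a recording convention that neither document states.

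A reader might go further and infer that these events disappear from every safety table. The documents do not support that: the outputs in SAP 2.5.4 do not use the flag, some rows are worded AE, and the events stay in the listings. A reader might also infer that the total TEAE count can only be too low. That does not follow either, because the imputation in SAP 2.1.2 pushes in the opposite direction.

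**Conclusion.** The point holds in limited form. SAP 1.5.1 is narrower than Protocol 7.2.4.1.2 on a named safety endpoint, and nothing else in the SAP repairs it. The loss is conditional: it affects only AEs that start between consent and injection, are ongoing at injection, worsen afterwards and are not re-entered as new AEs. The number is unknown and probably small, given a window of at most 14 days; the rates used above are assumptions, not estimates. Per subject, the effect on overall TEAE incidence is at most 1.1 points in the active arm and 3.3 in the placebo arm. The net error in total counts has no established sign. The primary efficacy result is not touched. The sentence should still be corrected, because otherwise the TEAE tables would not follow the protocol's own definition.

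**What to change.** Replace the sentence in SAP 1.5.1 with wording such as: *A TEAE is an AE with onset at or after study treatment, or an AE with onset before treatment that increases in severity after treatment.*

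State how worsening after injection is captured: either a new AE record with its own onset, or a date of worsening on the existing record. Without one of these the second limb cannot be programmed. If a single record is kept, also state that time to onset and duration in SAP 2.5.2 run from the date of worsening; otherwise time to onset would be negative for these events.

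The cost is one SAP sentence and a line in the eCRF completion guidance, plus one date field if the single-record route is chosen. Design, endpoints and sample size do not change. It should be settled before database lock, when Protocol 9.1 requires the SAP to be final; a change to a finalized SAP has to be documented in the clinical study report.
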